Appendix B: Definitions

Non-study Specific Definitions

Adverse Event (AE)

Any untoward medical occurrence, unintended disease or injury, or untoward clinical signs (including abnormal laboratory findings) in subjects, users or other persons, whether or not related to the investigational medical device under clinical investigation.

This definition includes events related to the investigational medical device (ADO II AS) as well as events related to the procedures involved in the clinical protocol.

Serious Adverse Event (SAE)

An adverse event that led to:

- Death
- A serious deterioration in the health of the subject, that either resulted in:
 - A life-threatening illness or injury OR
 - A permanent impairment to a body structure or a body function OR
 - An in-patient or prolonged hospitalization OR
 - A medical or surgical intervention to prevent life-threatening illness or injury or permanent impairment to a body structure or a body function OR
 - A malignant tumor
- Fetal distress, fetal death or a congenital abnormality or birth defect
- A planned hospitalization for a pre-existing condition, or a procedure required by the CIP is not considered a serious adverse event.

Adverse Device Effect (ADE)

An adverse event related to the use of an investigational medical device.

This definition includes adverse events resulting from insufficient or inadequate instructions for use, deployment, implantation, installation, or operation, or any malfunction of the investigational medical device.

This definition includes any event resulting from the use error or from intentional misuse of the investigational medical device.

Serious Adverse Device Effect (SADE)

Adverse device effect that has resulted in any of the consequences characteristic of a serious adverse event.

Unanticipated Adverse Device Effect (UADE)

As defined in 21 CFR §812.3, unanticipated adverse device effects (UADE) are defined as any serious adverse effect on health or safety or any life-threatening problem or death caused by, or associated with, a device, if that effect, problem, or death was not previously identified in nature, severity, or degree of incidence in the CIP or application (including a supplementary plan or application), or any other unanticipated serious problem associated with a device that relates to the rights, safety, or welfare of subjects.

Study Specific Definitions

Related:

The adverse event is related to the study device/procedure – i.e. an event that follows a reasonable temporal sequence from administration of the study intervention, follows a known or expected response pattern to the suspected intervention, that is confirmed by improvement on stopping and reappearance of the event on repeated exposure and that could not be reasonably explained by the known characteristics of the subject's clinical state.

In summary, the **AE is related** to the study device (ADO II AS) or procedure if the event satisfies all of following criteria:

- Has a reasonable temporal relationship to intervention (e.g. device implant)
- Could not readily have been produced or explained by the subject's clinical state or have been due to environmental or other interventions
- Follows a known pattern of response to intervention
- Disappears or decreases with reduction in dose or cessation of intervention and recurs with re-exposure

Attempted ADO II AS Device Implant

Insertion of the TorqVue™ LP Catheter (9-TVLPC4F90/080) into the vasculature of the subject.

Major Complication

Major complications are defined as device (ADO II AS) or procedure-related adverse events resulting in any of the following:

- death,
- life-threatening adverse event,
- persistent or significant disability/incapacity, and/or
- a major open surgical intervention which is performed by a surgeon under general anesthesia

Examples of Major Complications:

- Device or procedure related events leading to death
- Cardiac perforation requiring percutaneous (e.g., pericardiocentesis) or open surgical intervention
- Cardiac tamponade
- Embolization requiring open surgical procedure (e.g., open heart surgery or femoral vessel cutdown procedure) to retrieve the device
- Persistent hemodynamic instability requiring emergency cardioversion/defibrillation therapy or emergency blood transfusion and/or institution of inotropic therapy
- Excessive blood loss or hemolysis requiring transfusion ≥ 20 cc/kg
- Persistent or worsening respiratory instability
- Cerebral or pulmonary embolism
- Persistent cardiac arrhythmia requiring a pacemaker
- Arteriovenous fistula requiring open surgical intervention
- False aneurysm of the femoral artery requiring surgical intervention
- Femoral vessel thrombophlebitis treated with intravenous antibiotics
- Infection of the device (bacterial endocarditis)

Minor Complication

Minor complications are defined as device (ADO II AS) or procedure-related adverse events that do not fit the definition of a major complication. These will include adverse events which may require medical intervention but are not life threatening, are not likely to have long-term (> 6 months) sequelae, and do not require long term (> 6 months) therapy. The following are examples of adverse events considered to be minor complications:

Examples of Minor Complications:

- Embolization that occurs intra-operatively where the device is retrieved using a transcatheter approach (e.g., using a snare) without needing to perform an open surgical procedure, such as open heart surgery or an open femoral vessel cutdown procedure.
- Reduced peripheral pulse (reversible) that can be managed with anti-thrombotic therapy (e.g., heparin, Aspirin)
- Cardiac perforation not requiring percutaneous (e.g., pericardiocentesis) or open surgical intervention
- Transient cardiac arrhythmia that is managed successfully with cardioversion or medication
- Hematoma of the groin not requiring open surgical intervention

[REDACTED]

[REDACTED]

[REDACTED]

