6.1 Endpoints

6.1.1 Primary Safety Endpoint (IDE and CAP)

The primary safety endpoint is the rate of major complications through 180 days after an attempted ADO II AS device implant (refer to Appendix B for definition).

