8.2 Adverse Event Reporting

Safety surveillance within this trial (and the safety reporting performed by the investigator), starts as soon as the subject is enrolled. The safety surveillance and the safety reporting will continue until the last investigational visit has been performed, the subject is deceased, the subject/investigator concludes his/her participation into the clinical investigation or the subject withdrawal from the clinical investigation.

All adverse event data required to be reported will be collected throughout the clinical investigation and will be reported to the Sponsor on a CRF.

Adverse events will be monitored until they are adequately resolved or the subject has ended his/her participation in the trial, whichever comes first. The status of the subject's condition should be documented at each visit.

For the purposes of this clinical investigation the following events will be reported (see **Appendix B** for definitions):

- Unanticipated adverse device effects
- All adverse events viewed/interpreted by investigator to be potentially related to either a) the implant procedure or b) the study device (ADO II AS) regardless of seriousness

Note – If relatedness is unknown or cannot be determined, then the event must be reported.

Note – if a procedure is abandoned and a non-study device is used to close the PDA, adverse events associated with the non-study device will not be reported.

Records relating to the subject's subsequent medical course must be maintained and submitted (as applicable) to the Sponsor until the event has subsided or, in case of permanent impairment, until the event stabilizes and the overall clinical outcome has been ascertained. Adverse events will be monitored until they are adequately resolved. The status of the subject's condition should be documented at each visit.

SAE Reporting

Reportable adverse events that are deemed by the investigator to be serious should be reported to the Sponsor as soon as possible but no later than outlined below.

Clinical Site	Reporting timelines
All Sites	SAEs must be reported to the Sponsor no later than 3 calendar days from the day the site personnel became aware of the event or as per the investigative site's local requirements, if the requirement is more stringent than those outlined above.

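### Read literally, Appendix B's test for relatedness keeps a device effect that is new in nature out of the primary safety rate, and no visible rule says how to count events of undetermined relatedness

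*Combined protocol and SAP*

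**What the plan says.** Section 6.1.1 sets the endpoint: "The primary safety endpoint is the rate of major complications through 180 days after an attempted ADO II AS device implant". Appendix B then restricts what can be counted: "Major complications are defined as device (ADO II AS) or procedure-related adverse events resulting in any of the following". Minor complications carry the same restriction.

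Appendix B defines Related twice, in a narrative sentence and in a list. The list applies "if the event satisfies all of following criteria". The four criteria are:

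1. a reasonable relationship in time;
2. no ready alternative explanation: "Could not readily have been produced or explained by the subject's clinical state or have been due to environmental or other interventions";
3. "Follows a known pattern of response to intervention";
4. abatement when the intervention stops and recurrence on re-exposure.

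The narrative version of the third criterion is slightly wider: "follows a known or expected response pattern to the suspected intervention".

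The same appendix defines a UADE as a serious effect caused by or associated with the device, "if that effect, problem, or death was not previously identified in nature, severity, or degree of incidence in the CIP" or the application. Section 8.2 makes UADEs reportable and adds, for other events: "If relatedness is unknown or cannot be determined, then the event must be reported". Section 5.9.2 gives an independent clinical events committee (CEC) the review of all reportable events and the adjudication of major and minor complications, under a charter that is not among the documents.

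**The concern.** Two neighbouring definitions pull against each other. The UADE definition recognises that the device may cause a serious harm nobody had identified. The Related definition requires the harm to match a pattern already known or expected. A harm that is new in kind can satisfy the first and fail the second, and the primary safety rate depends on the second.

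The reporting rule in 8.2 is also wider than the counting rule. It takes in events of unknown relatedness, but nothing visible says what happens to them in the endpoint.

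The setting makes both gaps relevant. Section 2.4.1 says no approved device exists for PDA closure below 5 kg or 6 months of age, so the stock of known patterns is limited. Section 4.5.2 admits infants from 700 g. Section 7.3 asks physicians to watch for nickel-related events, especially below 6 kg. Section 2.1 associates a significant PDA in premature infants with respiratory disease, haemorrhage and death, and Appendix B lists respiratory instability among its examples of major complications. Events whose cause is hard to assign are therefore foreseeable. The known-pattern requirement can only remove events, so its effect on the rate can only be downward.

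**Working it through.** **Definitions side by side.** There is no stated figure to reproduce: the sections on sample size and success criteria are not visible. The main check is to take each class of event through the four criteria.

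| Event class | Reportable under 8.2? | Known-pattern criterion | Outcome for the primary rate, as written |
|---|---|---|---|
| Serious device effect new in nature | Yes (UADE) | Fails | Not related, so not a major complication |
| UADE unanticipated only in severity or incidence | Yes (UADE) | Can pass | Not excluded by this criterion |
| Relatedness unknown or undeterminable | Yes | Not the main obstacle | Not shown to meet all criteria, chiefly the alternative-explanation one; no visible counting rule |

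The wider narrative phrase does not rescue the first class, because an effect new in nature is ordinarily neither known nor expected.

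The re-exposure criterion is more restrictive still. A one-time permanent implant offers almost no occasion for withdrawal and re-exposure. Yet Appendix B lists tamponade, perforation needing intervention and surgically retrieved embolization as major complications. Removing that criterion alone would leave the known-pattern problem in place.

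**Size of one event.**

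- Inputs: N = 40 and a minimum of 15 subjects at or below 2 kg, both from Section 4.1; exact binomial 95% interval from Section 6.1.1.1. The event counts are assumed, and 40 is used because the final sample size is not visible.
- Formula for x events in n: lower limit = Beta quantile at 0.025 with parameters (x, n − x + 1), or 0 if x = 0; upper limit = Beta quantile at 0.975 with parameters (x + 1, n − x).
- For x = 0 the upper limit reduces to 1 − 0.025^(1/n): with n = 40 this is 8.8%, and with n = 15 it is 21.8%.

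| n | Events counted | Rate | Exact 95% CI |
|---|---|---|---|
| 40 | 0 | 0% | 0 to 8.8% |
| 40 | 1 | 2.5% | 0.1 to 13.2% |
| 40 | 2 | 5.0% | 0.6 to 16.9% |
| 15 | 0 | 0% | 0 to 21.8% |
| 15 | 1 | 6.7% | 0.2 to 31.9% |

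At n = 40 each omitted event changes the rate by 1/40 = 2.5 percentage points. The upper limit rises by 13.2 − 8.8 = 4.4 points for the first event and 16.9 − 13.2 = 3.7 points for the second.

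**Chance that it arises.** The documents give no rate for events of these kinds. For an assumed per-subject rate q, the chance of at least one is 1 − (1 − q)^n.

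| q (assumed) | n = 40 | n = 15 |
|---|---|---|
| 1% | 33% | 14% |
| 2.5% | 64% | 32% |
| 5% | 87% | 54% |

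The documents do not say where in this range, or outside it, the true rate lies.

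**The case against.** The strongest reply is that the affected class is narrow. Section 7.1.1 lists dozens of anticipated effects, including death, embolization, erosion, perforation, thrombus, haemolysis and nickel toxicity. An effect absent from the plan may still follow a pattern known from other occluders or from catheterization. This stands: it limits how often the problem will occur, but does not remove the contradiction.

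A second reply is that the four criteria look like a generic causality template. The listed examples of major complications could not sensibly pass the re-exposure test, so the list may not be meant as a literal bar. Adjudication rests with the CEC, and its charter or redacted text near the endpoint may hold a counting rule. This too has force, and it is why the point is confined to the definitions as written. Any such rule would still have to be reconciled with Appendix B.

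Third, these events are not lost to the trial. They are reported and reviewed by the CEC, adverse events are summarised, and deaths are tabulated under Section 6.1.4. That is correct; only the primary rate is at issue.

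A reader might infer something stronger: that every UADE and every event of undeterminable cause is barred by the known-pattern criterion, and that such events also fall outside the adverse device effect categories. The documents do not support this. A UADE may be unanticipated in severity or incidence alone and still follow a known pattern. Undeterminable events fail mainly on alternative explanation, so relaxing the known-pattern criterion would not change their status. The adverse device effect definitions stand among the non-study-specific definitions, and nothing visible applies the four-part test to them.

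**Conclusion.** The point holds in a limited form. As written, a serious device effect new in nature is reportable as a UADE but is not a major complication, because the definition of Related demands a known or expected pattern. Events of undetermined relatedness are a separate gap: they are reportable, they do not meet the all-criteria test, and they have no visible counting rule.

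For an effect new in nature, the omission can only lower the safety rate. One event that otherwise qualifies is worth 2.5 points at N = 40, and about 4 points on the upper confidence limit when few events are counted. How many such events will occur is unknown.

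The conclusion rests on a literal reading of the definition, on 40 as an assumed denominator, and on the visible text alone. It does not show that the CEC would in practice leave such an event out.

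**What to change.** 1. In Appendix B, in both the narrative sentence and the list, make a known or expected pattern supporting evidence for relatedness and not a required condition. Correct the re-exposure criterion in the same edit; otherwise it continues to exclude almost everything.
2. State that an event the CEC adjudicates as a UADE is treated as related and is then classed major or minor by its consequence.
3. For events of undetermined relatedness, keep the primary rate on CEC-adjudicated related events. Add a prespecified sensitivity analysis that counts them as related, and report how many there are. Placing them all in the primary rate would risk loading an uncontrolled trial in premature infants with background morbidity, so a sensitivity analysis is the more proportionate choice.
4. Bring the CEC charter into line with these rules.

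The cost is a few sentences in Appendix B, one added analysis and a matching change to the charter. No new data are needed, because these events are already reported and reviewed. The downside is that the reported major complication rate may be slightly less favourable.

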5.9.2 Clinical Events Committee (CEC)

An independent CEC will be responsible for providing review and adjudication of pre-defined clinical events, including major and minor complications, deaths, or other events or endpoints as outlined in the CEC Charter. The CEC is responsible for reviewing all reportable Adverse Events as defined in section 8.2.

The CEC will also advise the Sponsor regarding the continuing safety of subjects and those yet to be recruited, as well as the continuing validity and scientific merit of the clinical investigation. CEC members will not be investigators in the clinical investigation. At any time during the investigation, the CEC may offer opinions or provide formal recommendations concerning aspects of the study that impact subject safety (e.g. safety-related protocol changes or input regarding study-related adverse event rates).

The primary function, responsibilities and membership of the CEC will be described in detail in a CEC charter.

6 Statistical Considerations

The following section describes the statistical methods for the clinical investigation and justification of the design. For the Primary and Secondary Endpoints, pivotal IDE subjects will be analyzed separately from CAP subjects.

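### Appendix B's relatedness test requires recurrence on re-exposure, which a one-time implant can almost never show; applied as written, it pushes the primary safety rate down

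*Combined protocol and SAP*

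**What the plan says.** The study-specific part of Appendix B defines when an adverse event is related to the device or the procedure. A narrative sentence includes, among its conditions, "that is confirmed by improvement on stopping and reappearance of the event on repeated exposure". A summary then classes the event as related to the device "or procedure if the event satisfies all of following criteria", followed by four bullets. The fourth is "Disappears or decreases with reduction in dose or cessation of intervention and recurs with re-exposure".

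The same appendix builds both complication classes on relatedness:

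- "Major complications are defined as device (ADO II AS) or procedure-related adverse events resulting in any of the following", followed by death, life-threatening events, lasting disability and major open surgery.
- "Minor complications are defined as device (ADO II AS) or procedure-related adverse events that do not fit the definition of a major complication".

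The examples of major complications include related events leading to death, cardiac tamponade, and "Embolization requiring open surgical procedure (e.g., open heart surgery or femoral vessel cutdown procedure) to retrieve the device".

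Sections 4.4.1 and 6.1.1 make the rate of major complications through 180 days after an attempted implant the primary safety endpoint. Section 6.1.1.1 reports it as a proportion with an exact binomial 95% confidence interval.

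**The concern.** Improvement on withdrawal and recurrence on re-exposure are causality tests suited to a drug that can be stopped and restarted. Here the intervention is a nitinol occluder left in the duct (Section 3.1.2). A criterion that nearly every true device event must fail should not be a necessary condition for counting that event.

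What is at stake is the numerator of the primary safety endpoint. Relatedness is required for a complication of either class, so a failing event is not downgraded from major to minor; it disappears from both. The criterion can remove true events but cannot add false ones, so any error favours the device. The study has a single arm (Section 4.1), so there is no comparator in which the same misclassification could offset it.

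**Working it through.** The visible documents contain no figure that depends on this definition: Sections 6.2 to 6.6 are redacted, as are parts of 4.4.1 and 6.1.1.1. There is nothing to reproduce. The check has two parts.

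**1. The definition against its own examples**

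| Listed major complication | Improves on cessation? | Recurs on re-exposure? |
|---|---|---|
| Related event leading to death | No | No |
| Cardiac tamponade | Not by stopping an implant | Would not be deliberately re-provoked |
| Embolization needing open retrieval | Possibly, once the device is out | Only if another device were placed and also embolized |

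The fourth bullet requires both columns. None of these examples can be expected to satisfy both, yet all three are listed as major complications. No visible text waives the criterion or says whether the definition or the example list prevails.

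**2. Possible size**

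Inputs from the documents: n = 40, the number of subjects with 6 months of follow-up that triggers the PMA submission (Section 4.1), and the exact 95% interval (Section 6.1.1.1). The event counts, true rates p and rejected fractions f below are assumptions.

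Exact limits for x events in n subjects: lower = Beta quantile(0.025; x, n − x + 1); upper = Beta quantile(0.975; x + 1, n − x). For x = 0 the lower limit is 0 and the upper limit is 1 − 0.025^(1/40) = 8.8%.

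| Counted events | Estimate | Exact 95% CI |
|---|---|---|
| 0/40 | 0% | 0 to 8.8% |
| 1/40 | 2.5% | 0.1 to 13.2% |
| 2/40 | 5.0% | 0.6 to 16.9% |
| 4/40 | 10.0% | 2.8 to 23.7% |

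Full application of the fourth criterion turns every row into the first.

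For partial application, suppose a fraction f of true events is rejected. The counted rate is q = p(1 − f), the expected count is 40q, the chance that none is counted is (1 − q)^40, and the downward bias is p − q. Coverage is the probability that the reported interval contains the true p.

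| p | f | Expected count | P(none counted) | Bias (points) | Coverage of p |
|---|---|---|---|---|---|
| 2.5% | 0 | 1.0 | 36% | 0 | 98.3% |
| 2.5% | 0.5 | 0.5 | 60.5% | 1.25 | 99.8% |
| 2.5% | 1 | 0 | 100% | 2.5 | 100% |
| 5% | 0 | 2.0 | 13% | 0 | 98.6% |
| 5% | 0.5 | 1.0 | 36% | 2.5 | 99.95% |
| 5% | 1 | 0 | 100% | 5 | 100% |
| 10% | 0 | 4.0 | 1.5% | 0 | 97% |
| 10% | 0.5 | 2.0 | 13% | 5 | 87% |
| 10% | 1 | 0 | 100% | 10 | 0% |

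At 2.5% and 5% the interval still contains the truth. The harm there is an estimate that is too low and, comparing 0/40 with 2/40, an upper limit about half as high (8.8% against 16.9%). At 10% with full rejection the interval excludes the truth.

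**The case against.** The strongest reply is that nobody would apply the criterion literally. The example list would then be nearly empty, which the authors cannot have meant, and an independent committee adjudicates the events. Reporting is also broad: "If relatedness is unknown or cannot be determined, then the event must be reported" (Section 8.2), and "The CEC is responsible for reviewing all reportable Adverse Events as defined in section 8.2" (Section 5.9.2). Much of this stands. Excluded events should remain visible in the adverse event and death summaries, and the bias may be nil. But reporting rules protect visibility, not classification. A committee that follows the examples departs from the written definition, with no visible rule telling it to.

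Other points against the concern:

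- The summary sentence says if, not only if, so it could be read as a sufficient condition. The narrative sentence above it offers the same elements as the meaning of related, which supports the necessary reading.
- Appendix B's adverse device effect entry covers events arising from deployment, implantation or malfunction and asks for no recurrence. It does not waive the fourth criterion; it adds a second, inconsistent standard.
- Improvement after retrieval is sometimes observable, and a repeat deployment could rarely act as re-exposure. That is true, so the test is almost never, rather than never, satisfiable.
- Two of the remaining three criteria are also strict: a known response pattern, and no ready explanation in the subject's clinical state. That is fair, but they can be applied to an implant; the fourth cannot.
- The CEC charter is not in the documents and nearby text is redacted. Either might settle the matter in practice, but the visible wording would still conflict.

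**Conclusion.** The concern holds. As written, the definition of related includes a condition that a once-implanted device essentially cannot meet, it conflicts with the examples that follow it, and it governs the primary safety numerator. The direction of any error is certain: downward. Its size cannot be derived from the documents. It ranges from nil, if the CEC works from the examples, to the whole true rate, if the criterion is applied strictly. The figures for 40 subjects are illustrations on assumed counts, rates and rejection fractions. The finding that the interval misses the truth altogether needs both an assumed true rate of 10% and complete rejection. This should be fixed: confidence in the wording defect is high, while its effect on the reported rate is conditional.

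**What to change.** - Delete the fourth bullet of the definition and the matching clause in the narrative sentence. Leave the other three criteria unchanged.
- Align the CEC charter and the example list with the amended definition, so that one standard governs adjudication.
- Have the CEC re-review any reported event that was classed as not related because of the deleted criterion.
- As a sensitivity analysis only, also report the major-complication rate counting events of possible or undetermined relatedness. Section 8.2 already requires these to be reported. The visible text shows no relatedness grading, so the CEC may need to record that category.
- If pivotal events have been adjudicated before the wording changes, record the date and report the count under both wordings. Section 6.7 is written for departures from the statistical plan, but the same openness should apply to a primary endpoint definition.

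The cost is a wording amendment, a charter check and a limited re-review, with no new patients, visits or procedures. The safety rate may come out slightly less favourable. A change made after pivotal data exist is a declared change to a primary endpoint definition, which is why both counts should be shown.
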